1.1 Summary

[figure not shown]
Title:	A single-arm, prospective, single-center phase II clinical study to evaluate the efficacy and safety of nimotuzumab combined with concurrent chemoradiotherapy in elderly patients with locally advanced unresectable esophageal cancer
Study overview	The mortality rate of esophageal cancer is 77%, and this rate will be even higher in elderly patients with esophageal cancer. A safe and effective treatment method is urgently needed. Currently, Nimotuzumab has been approved for esophageal cancer indications in 9 countries. We plan to conduct a single-arm, prospective, single-center Phase II clinical study to explore the efficacy and safety of Nimotuzumab in elderly patients with locally advanced esophageal cancer. The study population is elderly patients with locally advanced unresectable esophageal cancer, and 50 people are planned to be enrolled.
Purpose	To evaluate the efficacy and safety of nimotuzumab combined with concurrent chemoradiotherapy in elderly patients with locally advanced unresectable esophageal cancer.
Endpoint	Primary endpoint: progression-free survival (PFS) Secondary endpoints: objective response rate (ORR), disease control rate (DCR), local disease control rate (LDCR), overall survival (OS), 1-year OS/PFS, 2-year OS/PFS, and AE/SAE incidence.
Study population	Inclusion criteria: All the following patients must be met to be included in this study 1.The subjects voluntarily participated in this study, signed the informed consent, had good compliance, and cooperated with the follow-up; 2.Age 75 and above , male or female;

	
3.ECOG score 0-1;
 
4.Esophageal cancer confirmed by histology or cytology;
 
5.According to the Response Evaluation Criteria for Solid Tumors (RECIST 1.1), there is at least one measurable lesion, and the measurable lesion should not have received local treatment such as radiotherapy (lesions located in the previous radiotherapy area can also be selected as target lesions if they are confirmed to have progressed and meet the RECIST1.1 criteria);
 
6.Patients with stage II-IVB according to AJCC (8th edition, 2018) (IVB included metastasis to the celiac trunk or supraclavicular lymph nodes only) who are not suitable for or refuse surgery can tolerate concurrent chemoradiotherapy and targeted therapy;
 
7.Expected survival time ≥ 12 weeks;
 
8.The major organs function normally, meet the following criteria:
 
1)Blood test:
 
 a.HBG ≥ 90 g/L; b.ANC $\geq 1.5 \times 10^9$ /L; c.PLT $\geq 80 \times 10^9$ /L; 
2)Biochemical tests:
 
 a.ALB ≥ 30 g/L; b.ALT and AST ≤ 2.5 ULN; if there is liver metastasis, ALT and AST ≤ 5 ULN; c.TBIL ≤ 1.5 ULN; d.Plasma Cr ≤ 1.5 ULN or creatinine clearance (CCr) ≥ 60 ml/min; 
9.Echocardiographic assessment: left ventricular ejection fraction (LVEF) \geq lower limit of normal value (50%);
 
10.Female of childbearing age must agree to use contraceptive measures (such as intrauterine devices, birth control pills or condoms)

--	---

	
during the study and within 6 months after the end of the study; the serum or urine pregnancy test is negative within 7 days before study enrollment, and they must be non-breastfeeding patients; male must agree to use contraceptive measures during the study and within 6 months after the end of the study.
 
Exclusion criteria: Those who meet any of the conditions will not be included in this study
 
 1.Received EGFR monoclonal antibody or EGFR-TKI within six months; 2.Participated in other interventional clinical trials within 30 days before screening; 3.Patients with serious concurrent diseases, such as heart failure, high-risk uncontrollable arrhythmias, severe myocardial infarction, refractory hypertension, renal failure (CKD-4 and above), thyroid dysfunction, mental illness, diabetes, severe chronic diarrhea (more than 7 bowel movements per day), or patients who are considered unsuitable to participate in this clinical study by the researchers; 4.Patients with brain metastases with symptoms or symptom control time of less than 3 months; 5.Have a history of other malignant tumors (except for cured cervical carcinoma in situ or basal cell carcinoma of the skin and other malignant tumors that have been cured for more than 5 years); 6.The presence of active infection or active infectious disease; 7.Patients with multi-segment esophageal malignant tumors or signs of esophageal fistula or perforation; 8.Patients whose tumors have invaded important blood vessels as shown by imaging or who are judged by the researchers to be very likely to invade important blood vessels and cause fatal hemorrhage during the follow-up study;
--	---

	
9.Those who are allergic to the drugs or their ingredients used in this program;
 
10.Peripheral neuropathy or hearing loss of grade 2 or higher according to the criteria of Common Terminology for Adverse Events (NCI CTCAE V5.0);
 
11.Pregnant or breastfeeding women;
 
12.Patients with a history of psychotropic drug abuse and unable to quit or patients with mental disorders;
 
13.Those who are considered unsuitable to participate in this study by the researcher;
 
14.Those who are unwilling to participate in this study or unable to sign the informed consent.

Stage	Stage II
Center	Department of Radiation Oncology, Jiangsu Province Hospital
Study intervention	
1.Radiation Therapy
 
The prescription dose required that 95% PTV and PTV-nd receive 50-60 Gy /25-30 F , with a single dose range of 2.0 Gy/F, 5 days a week, external beam radiation to the chest .
 
2.Treatment
 
S-1: 40-60 mg/m² , po, D1, BID, 5 weeks;
 
Nimotuzumab 400 mg, iv, D1, week 1;
 
Nimotuzumab 200 mg, iv, D8, QW, Week 2-5.

Study duration	The estimated time from the start of the study to the completion of data analysis is 40 months
Visit duration	The planned enrollment period for this study is 12 months, and the time required for each subject to complete all visits are 24 months.

1.2 Study flow chart

1.3 Study schedule

Project name	Screening/Baseline Period	Treatment period					EOT visit	Efficacy follow-up	Survival follow-up
	-w3-w0	D1	D8	D1 5	D2 2	D2 9	D29	D29 to PD Date	PD date to death
Informed consent	✓								
Check Inclusion and exclusion criteria	✓								
Baseline and demographic data	✓								
Vital signs and physical examination	◆	✓	✓	✓	✓	✓	✓		
ECOG PS	◆	✓	✓	✓	✓	✓	✓		
Quality of life ⁶	◆	✓	✓	✓	✓	✓	✓	✓	✓
Charlson Comorbidity Index	✓								
Nutritional status	✓								
Blood routine examination	◆	✓	✓	✓	✓	✓	✓	■	
Urinalysis	◆	✓	✓	✓	✓	✓	✓	■	
Bowel routine	◆	✓	✓	✓	✓	✓	✓	■	

Blood biochemistry test	◆	✓	✓	✓	✓	✓	✓	■	
Coagulation	◆	✓	✓	✓	✓	✓	✓	■	
Virological examination ¹	✓								
Pregnancy test (female subjects of childbearing age)	✓								
Electrocardiog- ram	◆	✓	✓	✓	✓	✓	✓	■	
Echocardiogra- phy	✓								
Imaging examination ²	✓	▲			✓			✓	
Radiation therapy		✓	✓	✓	✓	✓			
Combination medication ³	✓	✓	✓	✓	✓	✓	✓	✓	✓
Adverse event assessment ⁴	✓	✓	✓	✓	✓	✓	✓	✓	✓
Survival follow-up ⁵		✓	✓	✓	✓	✓	✓	✓	✓

◆ The examination results within 1 week can be used without repeating the measurement.

▲ The test results within 2 weeks before medication can be used without repeated measurements.

■ If there are any anomalies that have not been resolved before, evaluation will be conducted as needed

1. First, screen for HIV antibodies, five hepatitis B tests, hepatitis C antibodies, and human papillomavirus

(HPV) tests. When the test results indicate the possibility of active hepatitis B or C infection, further HBV DNA quantitative testing and HCV RNA quantitative testing are required to confirm the diagnosis;

2. The imaging assessment can be performed by esophageal angiography and chest and abdominal enhanced CT examination according to the doctor's choice (imaging examinations of the same part at different times should use the same detection technology as the baseline period). The evaluation sites are mainly the esophagus and mediastinal lymphatic drainage area, and other parts are evaluated as needed. After the screening evaluation, imaging evaluation is performed every 21 days during radiotherapy, within 1 week and 4 weeks after the end of radiotherapy, and every 12 weeks thereafter until the disease progresses or the subject is intolerant or withdraws. The examination time window is ± 7 days;

3. Record the name, dosage, start and end time of combined medications and treatments, as well as the reasons for combined medications and treatments;

4. Adverse events that have occurred will be followed until they disappear, improve or stabilize and the investigators believe that no further follow-up is required, including AEs that occur within 7 days after the screening period and SAEs that occur within 30 days after the end of radiotherapy;

5. Patients will be followed up for survival every 12 weeks after PD, and can receive telephone visits, including patient survival status and tumor treatment status. The specific cause of death will be recorded in detail when it involves the following factors (primary tumor recurrence, bleeding, perforation, new lesions; recurrence or new metastatic lymph nodes within and outside the region, etc.);

6. During the efficacy follow-up period, evaluation was only performed during the first two follow-up visits.

2. Introduction

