4.1.1 Screening period

●Definition: within 3 weeks before drug administration

●Content:

- 1) Sign the informed consent form;
- 2) Screening;
- 3) Demographic characteristics;
- 4) History of present disease;
- 5) Past medical history;
- 6) Combined treatment;
- 7) Body surface area (BSA);
- 8) Physical examination
- 9) Vital signs;
- 10) ECOG performance status: see 12.1. ECOG performance status scoring standards;
- 11) Nutritional status: see 12.4. Nutritional risk screening form (NRS 2002);
- 12) Quality of life: see 12.5. Quality of life score (QoL) of cancer patients;
- 13) Charlson Comorbidity Index: see 12.6. Charlson Comorbidity Index scoring criteria and calculation method;
- 14) Initial tumor imaging assessment:
 - a.Oral and intravenous contrast-enhanced CT (neck + chest + abdomen, and pelvis if necessary) is preferred;
 - b.Optional items include intraesophageal ultrasound, bone scan, esophageal fiber endoscopy, esophageal barium meal, PET/CT, etc.
- 15) Electrocardiogram (12 leads);
- 16) Laboratory examination of blood samples (hematology and

biochemistry);

17) Pregnancy test (female subjects of childbearing age);

18) Adverse events were observed and recorded.

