4.1.4 Efficacy follow-up period

- Definition: From the end date of radiotherapy (D29) to the PD date
- Frequency (except for special items): The first review is on the 28th day after completion (W9D5), and then every 12 weeks starting from W9D5 until disease progression, with a window period of ± 7 days.
- Content:
 - 1) Film degree exam;
 - 2) Observation and recording of adverse events (AEs occurring within 7 days after the end of radiotherapy and SAEs occurring within 30 days);
 - 3) Hematology, biochemistry, electrocardiogram (if there are previously unresolved abnormalities, blood samples and other laboratory evaluations are warranted);
 - 4) Combined treatment.

4.1.5 Survival follow-up period:

- Definition: From PD date to death/loss to follow-up
- Frequency: Once every 12 weeks, window period ± 7 days
- Content:

- 1.Understand and record the subject's survival status, cause of death and time (telephone follow-up is possible);
- 2.Combined treatment.

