5.1 Inclusion criteria

Patients must meet all of the following criteria to be eligible for this trial:

- 1)The patients voluntarily participated in this study, signed the informed consent, had good compliance, and cooperated with the follow-up;
- 2)Age 75 and above, regardless of gender;
- 3)ECOG score 0-1;
- 4)Esophageal cancer confirmed by histology or cytology;
- 5)According to RECIST 1.1 (see 12.2. Response Evaluation Criteria for Solid Tumors Version 1.1 for details), there is at least one measurable lesion, and the measurable lesion should not have received local treatment such as radiotherapy (lesions located in the previous radiotherapy area can also be

selected as target lesions if they are confirmed to have progressed and meet the RECIST 1.1 criteria);

6)Patients with stage II-IVB according to AJCC (8th edition, 2018) (IVB included metastasis to the celiac trunk or supraclavicular lymph nodes only) who are not suitable for or refuse surgery can tolerate concurrent chemoradiotherapy and targeted therapy;

7)Expected survival time \geq 12 weeks;

8)The major organs function normally, that is, they meet the following criteria:

●Blood test:

- a.HBG \geq 90 g/L;
- b.ANC \geq 1.5×10^9 /L;
- c.PLT \geq 80×10^9 /L;

●Biochemical tests:

- a.ALB \geq 30 g/L;
- b.ALT and AST \leq 2.5 ULN; if there is liver metastasis, ALT and AST \leq 5 ULN;
- c.TBIL \leq 1.5ULN;
- d.Plasma Cr \leq 1.5ULN or creatinine clearance (CCr) \geq 60ml/min;

9)Echocardiographic assessment: left ventricular ejection fraction (LVEF) \geq lower limit of normal value (50%);

10)Female of childbearing age must agree to use contraceptive measures (such as intrauterine devices, birth control pills or condoms) during the study and within 6 months after the end of the study; the serum or urine pregnancy test is negative within 7 days before study enrollment, and they must be non-breastfeeding patients; men must agree to use contraceptive measures during the study and within 6 months after the end of the study.

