1.2.2 Evaluation methods

The same techniques and methods should be used for baseline assessment and subsequent measurements of lesions. All lesions must be evaluated using imaging, except for lesions that cannot be evaluated by imaging but can only be evaluated by clinical examination.

Clinical lesions: Clinical lesions are considered measurable only when they are superficial and have a diameter of ≥ 10 mm (such as skin nodules). For patients with skin lesions, it is recommended to use color photos with a ruler to measure the size of the lesion for archiving. When lesions are evaluated by both imaging and clinical examination, imaging should be used as much as possible because it is more objective and can be reviewed repeatedly at the end of the study.

Chest X-ray: When tumor progression is an important research endpoint, chest CT should be used first because CT is more sensitive than X-ray, especially for new lesions. Chest X-ray is only applicable when the measured lesion has clear boundaries and the lungs are well ventilated.

CT, MRI: CT is currently the best available and repeatable method for evaluating efficacy. The definition of measurability in this guideline is based on CT scan slice thickness ≤ 5 mm. If the CT slice thickness is greater than 5 mm, the minimum measurable lesion should be twice the slice thickness. MRI is also acceptable in some cases (such as whole body scans).

Ultrasound: Ultrasound should not be used as a measurement method to measure lesion size. Ultrasound examinations are not repeatable after the measurement is completed due to their operation dependence, and the consistency of technology and measurement between different measurements cannot be guaranteed. If new lesions

are found using ultrasound during the trial, CT or MRI should be used for confirmation. If the radiation exposure of CT is considered, MRI can be used instead.

Endoscopy, laparoscopy: These techniques are not recommended for objective tumor evaluation, but they can be used to confirm CR when biopsy specimens are obtained and to confirm recurrence in trials where the endpoint is recurrence after CR or surgical resection.

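### No section requires CT at every tumour assessment: schedule note 2 leaves the modality to the doctor, so detection of progression can depend on which test is chosen

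*Protocol*

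**What the plan says.** Note 2 to the schedule in Protocol 1.3 is the main instruction on imaging: "The imaging assessment can be performed by esophageal angiography and chest and abdominal enhanced CT examination according to the doctor's choice". It adds a consistency rule, "imaging examinations of the same part at different times should use the same detection technology as the baseline period", and a statement of sites, "The evaluation sites are mainly the esophagus and mediastinal lymphatic drainage area, and other parts are evaluated as needed".

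Other sections touch the modality:

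- **4.1.1 Screening period:** "Oral and intravenous contrast-enhanced CT (neck + chest + abdomen, and pelvis if necessary) is preferred". It then adds "Optional items include intraesophageal ultrasound, bone scan, esophageal fiber endoscopy, esophageal barium meal, PET/CT, etc".
- **4.1.2 Treatment period:** imaging every 21 days, no modality named.
- **4.1.4 Efficacy follow-up period:** the imaging item reads only "Film degree exam".
- **5.1 Inclusion criteria:** under RECIST 1.1, "there is at least one measurable lesion". It need not be the esophageal primary.
- **Appendix 12.2:** item 1.1.1 sets measurability thresholds for CT, clinical examination and chest X-ray. Item 1.2.2 says "CT is currently the best available and repeatable method for evaluating efficacy", accepts MRI in some cases, and asks that a lesion be measured by the same method at baseline and later. No esophageal contrast study appears among its methods.

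Section 9.1 makes investigator-assessed PFS the primary endpoint.

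**The concern.** PFS here is dated by imaging unless the patient dies first, and there is no control arm in which a weakness in detection would also operate. If the test may vary between patients or visits, the recorded progression date depends partly on the test chosen, and the person choosing knows the treatment and judges progression.

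The conflict is also internal. The appendix that defines response and progression rests on CT. It says that where progression is an important endpoint, chest CT should come before chest X-ray because it is more sensitive, above all for new lesions. The schedule note does not carry that requirement into practice. At stake are the primary endpoint and the response-based secondary endpoints (ORR, DCR, LDCR).

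**Working it through.** The protocol gives no figure on this point and no formula applies. The check is to read the provisions together and see which situations they leave open.

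**Step 1. Is CT mandatory anywhere for tumour assessment?** Note 2 grants a choice, 4.1.1 states a preference, and 4.1.2 and 4.1.4 are silent. Appendix 12.2 ranks CT highest but does not say that it must be done at each visit. Section 6.1.2 outlines the target volume on enhanced CT, but that is radiotherapy planning and not a scheduled response assessment. So the answer is no.

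**Step 2. What is the other test?** The protocol calls it esophageal angiography. This is probably a translation of contrast esophagography, since barium studies appear in 4.1.1 and 6.1.2, but that reading is an inference. On either reading the test is absent from the measurement methods in Appendix 12.2. The appendix does not say outright that the test gives no measurement; that is inferred from its absence.

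**Step 3. Which patients are protected by the other rules?**

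| Situation at baseline | Rules that apply | Result |
|---|---|---|
| Primary is a target lesion measured on CT, with no contrast study done | Note 2 consistency rule; Appendix 12.2, item 1.2.2 | Both point to CT afterwards |
| Both CT and a contrast study done, primary a CT-measured target | Note 2 works by body part, so repeating either test could satisfy it; item 1.2.2 calls for CT | Note 2 read alone allows what the appendix does not |
| Both tests done, a node is the target and the primary is non-target | Item 1.2.2 keeps the node on CT; item 2.3.3 asks only for qualitative assessment of the primary | No measurement of the primary is needed, but note 2 still does not say that a CT must be done at the visit |
| Contrast study only | 5.1 with item 1.1.1 | Does not establish measurable disease by a listed method |

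The second and third rows hold the gap. They are plausible, because 4.1.1 permits a barium study alongside CT and 6.1.2 lists one among the images used in planning.

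**Step 4. What follows at a visit with the contrast study alone?** There is no CT of the primary, the mediastinal nodes or possible new sites. Under Appendix 12.2, item 2.4.2, a patient whose lesion is not imaged or measured is generally not evaluable at that time point. Yet 8.1.1 dates censoring from the last tumour assessment without saying which test qualifies. The visit could therefore be recorded as free of progression.

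**Step 5. Can the size be derived?** It would need the share of assessments done without CT and the share of progressions that the contrast study would miss. The protocol gives neither. It supplies only the spacing of follow-up visits, nominally 12 weeks (12 × 7 = 84 days). If one progression were missed at a follow-up visit and found at the next, that patient's date would move by about that interval. This is a delay for one patient and not an estimate of the shift in median PFS.

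**The case against.** The strongest reply is that the protocol, read as a whole, already leads to CT. Note 2 joins the two tests with *and*, so it may mean that both are done. Entry requires a measurable lesion, which a contrast study does not establish by any listed method. Two separate rules tie later examinations to the baseline technique, and note 2 names the mediastinal drainage area, for which the chest CT is the natural test of the two. The technique is also fixed at baseline, before outcomes are known.

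Much of this stands. A reader might infer that the doctor may simply choose an esophagram instead of CT, that the consistency rule then locks it in, and that such patients have no sum of diameters, no partial response and no measurable progression. The documents do not support that chain. The measurable-lesion criterion and the same-technique rules should hold a CT-measured target on CT. If a node is the target, the sum comes from the node and a non-target primary needs only qualitative assessment. New lesions still count as progression, and deaths count as PFS events without any scan.

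The reply does not close the gap. If both tests were required there would be nothing for the doctor to choose. The consistency rule secures sameness by body part, not adequacy, and where both tests exist at baseline it does not say which must be repeated. The site statement says what is mainly looked at, not by which method.

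**Conclusion.** The point holds in a limited form. CT is not required at every tumour assessment, the modality is left to the doctor, and the alternative named is not an Appendix 12.2 measurement method. The exposure is confined mainly to patients who had both tests at baseline and in whom only the contrast study is repeated at a later visit. There, detection of progression rests on the choice of an unblinded doctor.

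This assumes that esophageal angiography means a contrast study of the esophagus, and that sites may act on the schedule note without reading it against the appendix. No effect on median PFS or response rate can be stated from the documents. A reader might infer a known upward bias in PFS; the protocol gives no basis for quantifying one or for showing that it would occur. This is a cheap improvement to the primary endpoint's ascertainment and not a defect that invalidates the design.

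**What to change.** Reconcile note 2 in 1.3 with 4.1.1, 4.1.4 and Appendix 12.2, so that all of them say the following:

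- Contrast-enhanced CT is done at baseline and at every scheduled tumour assessment, with MRI where contrast CT is contraindicated.
- RECIST measurements are taken only from that examination.
- The esophageal contrast study may be added, but it cannot replace CT or by itself establish response or non-progression.

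Note 2 should also give the esophageal test its correct name, and 4.1.4 should name the examination in place of its present imaging item. The cost is a wording change and less local freedom in choosing the test. CT is already among the planned examinations.

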4.1.2 Treatment period

●Definition: First radiotherapy day W1D1 - last radiotherapy day W5D5

●Window period: treatment ± 2 days, imaging ± 7 days, pre-dose items -1 day.

●Content:

1)Before WxD1 administration

a.Body surface area (BSA);

b.Physical examination

c.Vital signs;

d.ECOG performance status score;

e.Blood samples and other laboratory evaluations (hematology and clinical chemistry);

f.Electrocardiogram (12 leads);

2)Administer nimotuzumab (see 6.1.2. Dosage and administration);

3)Administer Tegafur (see 6.1.2. Dosage and Administration);

4)Administer radiation therapy (see 6.1.2. Dosage and administration);

5)Observe and record adverse events;

6)Combined treatment;

7)Imaging examination: Review every 21 days after W1D1 (such as W1D22).

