7.1 Study intervention discontinuation

Suspension of study intervention does not mean suspension of the study, and subsequent study procedures should be completed in accordance with the provisions of the trial protocol. If clinically significant changes occur after enrollment (including but not limited to changes from baseline levels), the investigator will decide whether the subject management needs to be changed. Any new clinically relevant findings will be reported as adverse events (AEs).

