7.1.1 Criteria for discontinuation of study intervention

In the event of any of the following circumstances, the subject must discontinue the study intervention

- 1)If a clinically relevant event occurs that seriously affects the safety of the subject, the investigator or sponsor considers it necessary to terminate the intervention;
- 2)Imaging examinations to determine disease progression;
- 3)The subjects received other study drugs or chemotherapy during the clinical study;
- 4)Lack of compliance by subjects;

- 5)The subject becomes pregnant during treatment;
- 6)Elective surgery.

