7.1.3 Subject discontinuation/withdrawal from study

- 1)Patients may request to withdraw from the study at any time.
- 2)Researchers may ask subjects to terminate or withdraw from the study for the following reasons:
 - Pregnancy;
 - Poor compliance with study interventions;
 - If a clinical adverse event (AE), laboratory abnormality, or other medical condition occurs, continued participation in the study will not be in the best interest of the subject;
 - Disease progression requiring discontinuation of intervention;
 - The subject meets the exclusion criteria (new or previously undetected) and cannot continue to participate in the study;
 - Subjects are unable to receive regularly scheduled study interventions.
- 3)A subject to discontinue or withdraw from the study should be recorded in the case report form (CRF). Subjects who signed informed consent and underwent randomization but did not receive the study intervention can be replaced. Subjects who signed informed consent, underwent randomization, received the study intervention, and subsequently withdrew or were withdrawn/discontinued from the study cannot be replaced.

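### Schedule note 2 stops tumour imaging for undefined intolerance where 4.1.4 continues it to progression, and 7.1.3 lets treatment problems end study participation, so primary-endpoint scans can be lost for reasons linked to prognosis

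*Protocol*

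**What the plan says.** Imaging (Protocol):
- 1.3, note 2: after the radiotherapy period, scans are 12-weekly "until the disease progresses or the subject is intolerant or withdraws".
- 4.1.4: first review at W9D5, "then every 12 weeks starting from W9D5 until disease progression". The efficacy follow-up column of the schedule, with imaging ticked, likewise runs from D29 to the PD date.
- 4.1.2: the treatment period is "First radiotherapy day W1D1 - last radiotherapy day W5D5", so it ends before the 12-weekly scans begin.

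Stopping and leaving:
- 7.1: "Suspension of study intervention does not mean suspension of the study, and subsequent study procedures should be completed".
- 7.1.1: "In the event of any of the following circumstances, the subject must discontinue the study intervention"; one listed circumstance is "Lack of compliance by subjects".
- 7.1.3: "Researchers may ask subjects to terminate or withdraw from the study for the following reasons"; the list includes "Poor compliance with study interventions" and being unable to have the scheduled interventions.
- 6.3: for inadequate compliance, the only consequence considered is stopping the study drug.
- 7.1.2: early leavers should complete the necessary examinations. It names no continuing imaging.

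PFS dating (8.1.1): a death before progression counts at its date (item 3). A subject with neither event, or lost to follow-up, is closed at the last tumour assessment (items 4-5), and a subject with only a baseline scan at baseline (item 6).

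**The concern.** PFS is the primary endpoint, and progression is found only by scanning. For a subject judged intolerant who has not progressed, note 2 stops the scans and 4.1.4 continues them. The word has two readings. If it means intolerance of treatment, it acts in the first five weeks or so and can remove every post-treatment scan. If it means inability to undergo the examination, it removes little that could have been obtained. The protocol does not say which is meant.

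Section 7.1.3 opens a second route to the same loss. Poor compliance stops treatment under 7.1.1 and can end study participation under 7.1.3. Failure to receive scheduled treatment is in substance a treatment stop, yet 7.1.3 lists it as a reason to leave the study. No rule says which exit applies.

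Subjects aged 75 or over who cannot be treated plausibly have a different prognosis from those who can, so closing them at an early scan is unlikely to be uninformative. There is no control arm to share the distortion.

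**Working it through.** **1. Side by side.** Subject without progression, still consenting:

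| Situation | Note 2 | 4.1.4 and schedule column | 7.1 | 7.1.3 |
|---|---|---|---|---|
| Intolerant | scans stop | scans continue | procedures continue | not named |
| Treatment stopped for poor compliance | silent | scans continue | procedures continue | may leave study |
| Scheduled treatment cannot be given | silent, unless this is intolerance | scans continue | procedures continue | may leave study |

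The first row is a conflict. The other two are an unresolved choice.

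**2. Where PFS closes.** A subject who stops before the D22 scan and has no later one closes at baseline (item 6). One who stops just after D22 closes at about 3 weeks, and one who stops after W9D5 at 60 days or later. 60/30.4375 = 1.97 months.

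**3. Size, illustrative.** From 9.1: reference median 16 months, expected 18.2, gain 18.2 - 16 = 2.2 months, dropout 20% (41/0.80 = 51.25, so 52). Section 9.3.1 defines dropout as any failure to complete follow-up, so 20% is a ceiling for leavers of this kind. Assumed, not in the protocol: leaver share q = 10-20%, hazard ratio h = 1.5-2, exponential times, last scan t = 1.97 months.

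Hazard λ of the other subjects solves (1-q)e^(-16λ) + q e^(-16hλ) = 0.5, so the true overall median is 16.

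*No later event of a leaver is seen.* With S(t) = (1-q)e^(-λt) + q e^(-hλt), the Kaplan-Meier median is t + ln(2S(t))/λ.

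| q | h | λ | S(1.97) | Median read |
|---|---|---|---|---|
| 0.10 | 1.5 | 0.04153 | 0.9177 | 16.59 |
| 0.15 | 2 | 0.03883 | 0.9161 | 17.57 |
| 0.20 | 2 | 0.03742 | 0.9157 | 18.14 |
| 0.20 | 1 | 0.04332 | 0.9182 | 16.00 |

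Moving the last scan to 3 weeks raises 18.14 to about 18.4.

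*All later deaths captured, scans not, living leavers closed at the last scan (8.1.1 items 3-5).* A share of 0.3-0.5 of leavers' first events are deaths. In the rest, death follows unseen progression after a mean of 3-12 months. Simulation gives these medians over the three scenarios with h above 1:
- 24-month cut (the visit duration in 1.1): 15.6 to 16.5.
- 36-month cut: 15.9 to 17.3.
- Equal prognosis (q = 0.20, h = 1), 24-month cut: 14.8 to 15.4.

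The estimate can fall because leavers who die stay in the risk set and count, while those who live are removed at the early scan.

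*Between these.* If 30-50% of leavers' later first events are recorded as deaths and the rest never seen, the median reads 16.3 to 17.4 (16.0 to 17.1 with a 24-month cut). If all deaths are recorded, on average 6 months after unseen progression, and living leavers are kept to last contact, it reads 16.4 to 17.2. The second departs from items 4-5.

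**4. Scale.** With 52 subjects and a true median of 16, the 95% sampling range of the Kaplan-Meier median is about 10.2 to 22.6 months (20,000 simulated trials).

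**The case against.** Much of the case on the other side stands.

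- Of note 2's two extra stops, withdrawal is unavoidable, since a subject may leave at any time. Only intolerance conflicts with 4.1.4, and if it means inability to be scanned, even that is close to a wording difference.
- A reader might infer that 7.1 and 7.1.3 contradict each other. They do not: one concerns stopping the intervention, the other leaving the study, and 7.1.3 is permissive. Section 7.1.2 softens the effect, but it requires no scan after exit.
- A reader might count progression, pregnancy and safety events as further shared grounds. Progression costs no PFS data because the event has occurred, pregnancy is practically empty at 75 and over, and the safety grounds in 7.1.1 and 7.1.3 apply different tests.
- A reader might infer that nobody is contacted before PD, because note 5 and 4.1.5 speak of contact after PD. The schedule ticks survival follow-up from D1, and 4.1.4 provides visits before PD. The gap concerns subjects taken off the study.
- A reader might infer that the reported median will be too long. That needs later events to go unseen. With deaths captured and 8.1.1 followed, the shift is near zero or of either sign. Sampling error is larger than any case computed.

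What remains is a real conflict over when primary-endpoint scans stop. The protocol's own RECIST appendix (12.2, 2.4.4) asks for efforts to assess objective progression after treatment has ended, in line with 4.1.4 and 7.1. Sampling error shrinks with more subjects; this loss of information does not.

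**Conclusion.** The point holds as an inconsistency that can cause informative loss of progression data. Note 2 disagrees with 4.1.4, the schedule column and 7.1 about intolerant subjects, and 7.1.3 leaves open whether a treatment stop for poor compliance or undeliverable treatment also ends imaging.

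Its effect on the PFS median is uncertain in size and direction. It is upward if later events go unseen: up to about 2.1 months (18.14 - 16) at 20% leavers with twice the hazard, close to the planned gain of 2.2. It is about -0.4 to +0.5 months at a 24-month cut if deaths are captured. Leaver share, hazard ratio, last-scan date and death timing are all assumptions. The documents do not support a claim that the median will be overstated.

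The change is worth making before enrolment ends, because scheduled imaging and withdrawal rules belong in the protocol and an analysis plan cannot supply missing scans. Confidence is high on the text and low on the size.

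**What to change.** 1. In note 2, matching 4.1.4 and 7.1: scheduled tumour assessments continue, where feasible, until RECIST progression, death or withdrawal of consent to follow-up, whether or not study treatment continues. Delete the intolerance stop, or limit it to inability to undergo the examination.
2. In 7.1.3, separate stopping treatment from leaving the study. Subjects whose treatment stops for compliance, or because it cannot be given, stay in scheduled imaging and survival contact unless they withdraw consent. The sponsor should reconcile the passages on safety-related discontinuation without changing any clinical rule.
3. In note 5 and 4.1.5, state that survival contact also covers subjects who stop imaging or leave before PD. Contact alone does not replace the scans, as the results with deaths captured show.

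Cost: protocol wording, plus keeping scans and calls already scheduled. After W9D5 (day 60) the 12-weekly scans within 24 months fall on days 144, 228, 312, 396, 480, 564 and 648, so at most 7 per subject. Expected scans to the event, under the assumptions above: 4.6 leavers × 4.4 ≈ 20 in the trial (10%, hazard ratio 1.5) to 9.0 × 4.1 ≈ 37 (20%, hazard ratio 2). The burden falls on a small number of elderly subjects who stopped early, which is why the feasibility and consent limits should stay.
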